6.9.1. IM Dosing

Participants receiving CAB LA and/or RPV LA are anticipated to be at risk for development of virologic resistance if ART is interrupted. The time period during which participants are at risk for development of virologic resistance may be determined by the period between when drug levels fall below therapeutic values and when they fall below levels which exert selective pressure on HIV. This time period will vary by ART agent and is dependent upon effective concentration, inhibitory concentration, and half-life.

Plasma concentrations of both LA drugs may be measurable for more than one year following IM injections. Any interruption in IM dosing should be discussed with the Medical Monitor. Investigators should ensure that the participant initiates alternative highly active ART to minimize the risk of developing resistance as concentrations of CAB and RPV decline over time.

IM dosing is expected to occur during the week in which the participant's projected visit falls (as according to the date of the first injection). The first injections for participants from ATLAS on CAB LA + RPV LA Q4W will occur at Day 1. The first injections for participants transitioning from oral SOC are administered at Week 4b (can be performed as soon as lab results from Week 4a become available and should be performed where possible within 2 weeks of visit 4a), and the second injections are given at Week 8. Between the Week 4a and 4b visits, participants must continue daily treatment with oral CAB and RPV tablets.

Since the first injection visit (Day 1 or 4b) will determine the future injection visit schedule for participants, planning for the first injection visit date (within allowed visit windows) should take into consideration the availability of the participants to adhere to future visit windows (planned vacations, business trips, *etc.*).

CAB LA + RPV LA dosing for participants transitioning from SOC treatment is as follows:

All injections should be planned as single injections per drug.

6.9.1.1. IM injections every 4 weeks (Q4W):

Week 4b only - CAB LA 600 mg + RPV LA 900 mg, each given as 1 X 3 mL IM injection

Week 8 and Q4W thereafter - CAB LA 400 mg IM + RPV LA 600 mg IM every 4 weeks for 100 weeks, each given as 1 X 2 mL IM injection

At Week 4b, participants transitioning from SOC will return to the clinic, take the last dose of oral CAB 30 mg + RPV 25 mg, and receive the first CAB LA 600 mg + RPV LA 900 mg injections (within 2 hours of the final oral dose of CAB + RPV). The first injection visit with IM CAB LA + RPV LA at Week 4b can be performed once central lab results are available and safety parameters are reviewed from the Week 4a visit.

The second and third IM injections with CAB LA 400 mg and RPV LA 600 mg will be performed at Week 8 and Week 12. There will be a -7 day dosing window for the second and third IM injections such that the second injection occurs within the window of Week 7 and Week 8 but no later than Week 8 and the third injection occurs within the window of Week 11 and Week 12 but no later than Week 12. Subsequent injections with CAB LA 400 mg and RPV LA 600 mg will occur every 4 weeks (± 7 days) thereafter. In addition, starting after the Week 16 injection, efforts should be made to limit time between injection visits to a maximum of 5 weeks. The Medical Monitor must be contacted if the length of time between injections exceeds or is projected to exceed 5 weeks.

6.9.1.2. IM injections every 8 weeks (Q8W):

Week 4b – CAB LA 600 mg + RPV LA 900 mg IM, each given as 1 X 3 mL IM injection

Week 8 - CAB LA 600 mg + RPV LA 900 mg IM, each given as 1 X 3 mL IM injection

Week 16 and Q8W thereafter - CAB LA 600 mg + RPV LA 900 mg IM, every 8 weeks for 100 weeks, each given as 1 X 3 mL IM injection

At Week 4b, subjects will return to the clinic, take the last dose of their oral (CAB 30 mg + RPV 25 mg), and receive the first CAB LA (600 mg) + RPV LA (900 mg) injections (within 2 hours of the final oral dose of CAB + RPV). The first injection visit with IM CAB LA + RPV LA at Week 4b can be performed once central lab results are available and safety parameters are reviewed from the Week 4a visit.

The second loading injection will be administered at Week 8 (CAB LA 600 mg + RPV LA 900 mg, with subsequent injections (CAB LA 600 mg + RPV LA 900 mg) occurring every 8 weeks thereafter. The dosing window for the second injection allows administration between Week 7 and Week 8, but preferably not later than Week 8. After Week 16, a dosing window (± 7 days) for injections is allowed, but not preferred. Starting at the Week 16 injection, the interval between injection visits should be limited to a maximum of 9 weeks. If the length of time between injections exceeds, or is projected to exceed 9 weeks, the Medical Monitor must be contacted to discuss individual subject case management

Participants transitioning from ATLAS and currently receiving CAB LA + RPV LA Q4W

Patient transitioning from the ATLAS study and on CAB LA + RPV LA Q4W treatment will be randomized at Day 1 to either continue Q4W administration or transition to Q8W administration of CAB LA + RPV LA. The first injection visit for the ATLAS-2M study can be performed once the final central lab results from the ATLAS study are available and safety parameters have been reviewed. For participants who received three or more Q4W CAB LA + RPV LA injections within ATLAS, the transition from ATLAS to ATLAS-2M Day 1 dosing must occur 4 weeks (± 7 days) from the final injections received in ATLAS. For those who received less than three Q4W injections within ATLAS, this transition to ATLAS-2M Day 1 injections must occur within 4 weeks (-7 days) from the final ATLAS injections

Dosing for participants transitioning from CAB LA + RPV LA Q4W in ATLAS is as follows:

6.9.1.3. IM injections every 4 weeks (Q4W) (Q4W from ATLAS Q4W):

Starting at Day 1, all injections will continue with the maintenance dose of CAB LA 400 mg and RPV LA 600 mg administered every 4 weeks (± 7 days). In addition, efforts should be made to limit time between injection visits to a maximum of 5 weeks. The

Medical Monitor must be contacted if the length of time between injections exceeds or is projected to exceed 5 weeks.

6.9.1.4. IM injections every 8 weeks (Q8W) (Q8W from ATLAS Q4W):

Participants transitioning from ATLAS and receiving CAB LA + RPV LA Q8W will initiate dosing at the Day 1 visit:

Day 1- CAB LA 600 mg + RPV LA 900 mg IM, each given as 1 X 3 mL IM injection

Week 8 and Q8W thereafter- CAB LA 600 mg + RPV LA 900 mg IM, each given as 1 X 3 mL IM injection

The second injection will be administered at Week 8 (CAB LA 600 mg + RPV LA 900 mg, with subsequent injections (CAB LA 600 mg + RPV LA 900 mg) every 8 weeks thereafter. The dosing window for the second injection allows administration between Week 7 and Week 8, but preferably not later than Week 8. After Week 16, a dosing window (± 7 days) for injections is allowed, but not preferred. Starting at the Week 16 injection, the interval between injection visits should be limited to a maximum of 9 weeks. If the length of time between injections exceeds, or is projected to exceed 9 weeks, the Medical Monitor must be contacted to discuss individual subject case management.

Any request for the visit/dosing to occur outside of the allowed window must be discussed and agreed with the Medical Monitor prior to dosing. In the event of a late dose, a revised dosing schedule for subsequent dosing may be required and will be communicated to the site staff at the time of approval for continued dosing. Temporary switch to oral dosing of CAB and/or RPV may be an option based on individual participant circumstance as described in Section 6.8.

See the SPM for scheduling guidance and further information and examples.

Note: All decisions regarding dose interruption/ resumption must be discussed with the Medical Monitor in advance.

6.9.2. Oral Dosing

The Week 4a Visit during the Oral Lead-in Phase for participants transitioning from SOC is expected to occur 4 weeks (± 3 days) after to the Day 1 Baseline visit. However, the number of tablets dispensed should be considered when scheduling the next visit.

Any interruption in therapy (scheduling conflicts, life circumstances, *etc.*) during any oral dosing period that is greater than 7 consecutive days must be discussed with the Medical Monitor prior to resumption of therapy. The Medical Monitor must be contacted upon site staff becoming aware of resumption in therapy, if therapy was resumed without prior approval.

Visits for participants in LTFU are expected to occur as projected according to the last injection.

6.10. Discontinuation of Study Treatment

Participants unable to manage drug toxicity or tolerate investigational product (IP, either formulations of CAB or RPV) must have IP discontinued. Any participant receiving at least one dose of CAB LA and /or RPV LA who discontinue IP / Withdraw will initiate treatment with HAART enter the LTFU Phase for 52 weeks of follow up (see Section 4.2.4).

6.11. Treatment of Study Treatment Overdose

For participants receiving Oral CAB, any tablet intake exceeding a total daily dose of 30 mg will be considered an overdose. For participants receiving oral RPV, any dose exceeding a total daily dose of 25 mg will be considered an overdose.

For CAB LA and RPV LA, any single dose in excess of the studied doses will be considered an overdose.

Should IM maladministration, specifically overdose or inadvertent IV dosing, be suspected at any time, the participant will stay onsite for approximately 2-3 hours post dose for safety monitoring and an ECG will be performed at 2 hours post dose. The Medical Monitor will be notified in the event of a suspected maladministration.

In the event of suspected maladministration, additional PK samples will be drawn at 2 hours post dosing for evaluation of CAB and RPV concentrations.

For the purposes of this study, an overdose is not an AE (refer to Section 11.6.1) unless it is accompanied by a clinical manifestation associated with the overdose. If the clinical manifestation presents with serious criteria, the event is a SAE (see Section 11.6.2).

If an overdose occurs and is associated with an adverse event requiring action, all study medications must be temporarily discontinued until the adverse event resolves.

The Investigator should use clinical judgement in treating overdose, as ViiV Healthcare is unable to recommend specific treatment.

In the event of an overdose the investigator or treating physician should:

1. Contact the Medical Monitor immediately
2. Closely monitor the participant for adverse events (AEs)/serious adverse events (SAEs) and laboratory abnormalities until the IP can no longer be detected systemically (at least 5 days for oral CAB and oral RPV, and 52 weeks for CAB LA and RPV LA)
3. Obtain a plasma sample for pharmacokinetic (PK) analysis if possible within 2 days from the date of the last dose of study treatment if requested by the Medical Monitor (determined on a case-by-case basis).
4. Document the quantity of the excess dose as well as the duration of the overdosing in the CRF.

Decisions regarding dose interruptions or modifications will be made by the investigator in consultation with the Medical Monitor based on the clinical evaluation of the participant.

6.12. Treatment after the End of the Study

The investigator is responsible for ensuring that consideration has been given to the post-study care of the participant's medical condition, whether or not GSK is providing specific post-study treatment. Participants who have successfully completed 100 weeks of treatment will continue to have access to both CAB LA and RPV LA in the Extension Phase until study treatment is either locally approved and commercially available, the participant no longer derives clinical benefit, the participant meets a protocol-defined reason for discontinuation or until development of either CAB LA or RPV LA is terminated.

6.13. Concomitant Medications and Non-Drug Therapies

Participants must be advised to notify their Investigator of any current or proposed concomitant medication, whether prescribed or over-the-counter, because of the potential for interactions between such treatments and the study medications. Concomitant medications (prescription and non-prescription) will be permitted during the course of the study at the investigator's discretion (except for prohibited medications described in Section 6.13.2) and should be administered only as medically necessary during the study. All concomitant medication, blood products, and vaccines taken during the study will be recorded in the eCRF. The minimum requirement is that the drug name, route, and the dates of administration are to be recorded.

Any medication or vaccine (including over-the-counter or prescription medicines, vitamins, and/or herbal supplements) that the participant is receiving at the time of enrollment or receives during the study must be recorded along with:

- reason for use
- dates of administration including start and end dates
- dosage information including dose and frequency

The Medical Monitor should be contacted if there are any questions regarding concomitant or prior therapy.

6.13.1. Permitted Medications and Non-Drug Therapies

Chemoprophylaxis for HIV-associated conditions is encouraged, if appropriate, at the discretion of the participant and their physician. All concomitant medications, blood products, and vaccines taken during the study will be recorded in the eCRF with dates of administration.

Because non-HIV vaccines may cause a temporary increase in the level of plasma HIV-1 RNA, it is recommended that a vaccine, if necessary, be given during or immediately after a scheduled visit after all laboratory tests have been drawn. This approach will

minimize the risk of non-specific increases in the level of plasma HIV-1 RNA at the next scheduled assessment.

Other IM injectables (with exceptions below) are permitted but must be administered away from the site of IP administration (should be spaced 2 cm or more away from site of IP injection).

Antacid and H2 Antagonist Use:

Since co-administration of oral CAB and RPV is required in this study, the most restrictive dosing requirements must be taken into consideration.

CAB oral administration only: Antacid products containing divalent cations (e.g., aluminium, calcium and magnesium) must be taken at least 2 hours before or at least 4 hours after CAB.

Concurrent administration of multivitamins is acceptable.

RPV oral administration only: Antacid products must be taken at least 2 hours before or at least 4 hours after RPV. H2-Receptor antagonists (e.g. cimetidine, famotidine, nizatidine, ranitidine) may cause significant decreases in RPV plasma concentrations. H2-receptor antagonists should only be administered at least 12 hours before or at least 4 hours after RPV. RPV should not be co-administered with proton pump inhibitors, such as esomeprazole, lansoprazole, omeprazole, pantoprazole, rabeprazole.

RPV: Administration of clarithromycin, erythromycin and telithromycin is not recommended with RPV due to possible increase in plasma concentration of RPV due to CYP3A enzyme inhibition. Where possible, alternatives such as azithromycin should be considered. Please refer to the local rilpivirine prescribing information for guidance regarding other drugs that are prohibited, should be used with caution, require dose adjustment, or increased clinical monitoring if taken with rilpivirine.

Drugs with a known risk of Torsade des Pointes (TdP) should be used with caution when on rilpivirine (see SPM for list of drugs associated with TdP).

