
34. Exposure to an experimental drug (with the exception of those in the ATLAS study including CAB, CAB LA, and RPV LA) or experimental vaccine within either 30 days, 5 half-lives of the test agent, or twice the duration of the biological effect of the test agent, whichever is longer, prior to Day 1 of this study;
 
35. Treatment with any of the following agents within 28 days of Screening:
 
 • radiation therapy; • cytotoxic chemotherapeutic agents; • tuberculosis therapy with the exception of isoniazid (isonicotinylhydrazid, INH); • anti-coagulation agents; • Immunomodulators that alter immune responses such as chronic systemic corticosteroids, interleukins, or interferons. Note: Participants using short-term (e.g. ≤ 21 days) systemic corticosteroid treatment; topical, inhaled and intranasal corticosteroids are eligible for enrolment. 
36. Treatment with an HIV-1 immunotherapeutic vaccine within 90 days of Screening
 
37. Treatment with any agent, except recognized ART as allowed above, with documented activity against HIV-1 within 28 days of study Day 1. Treatment with acyclovir/valacyclovir is permitted.
 
38. Use of medications which are associated with Torsade de Pointes. (See SPM for a list of relevant medications)
 
39. Current or prior history of etravirine (ETR) use
 
40. Current use of tipranavir/ritonavir or fosamprenavir/ritonavir
 
41. Participants receiving any prohibited medication and who are unwilling or unable to switch to an alternate medication. Note: Any prohibited medications that decrease CAB or RPV concentrations should be discontinued for a minimum of four weeks or a minimum of three half-lives (whichever is longer) prior to the first dose and any other prohibited medications should be discontinued for a minimum of two weeks or a minimum of three half-lives (whichever is longer) prior to the first dose

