- For any participant who withdraws prematurely from the Maintenance or Extension Phase during a planned in-clinic study visit, withdrawal assessments and procedures are to be performed (according to the Time and Events Table (Section 7.1) instead of the assessments for the active planned visit during which the withdrawal decision is made.

Withdrawal decision occurs between planned clinic visits:

- In the event that a decision to withdraw a participant occurs between clinic visits, participants will be instructed to return for an unscheduled withdrawal visit (within 4 weeks of the last Q4W LA injection or within 8 weeks of the last Q8W LA injection received) during which withdrawal assessments according to the Time and Events Table (Section 7.1) will be completed. For participants who received one or more injections of CAB LA+ RPV LA **withdrawal assessments must occur prior to initiation of the next ART regimen.**

If withdrawal coincides with the active planned Week 52 or Week 100 visits, HIV-1 RNA will only be assessed if the last HIV-RNA measurement from Week 48 or Week 96 was ≥ 50 copies per mL (i.e. retest for viral load blip). This will ensure that only the Week 48 or Week 96 viral load assessments or required retest will be counted towards the primary and secondary efficacy endpoint windows.

The in-clinic visit will be recorded as an unscheduled withdrawal visit with the following exception. A withdrawal visit and assessments coinciding with the planned Week 100 visit will be recorded as the Week 100 visit such that the participant can be considered a completer, consistent with the definition of study completer in Section 5.6.

Participants may be prematurely discontinued from the study treatment for any of the following reasons:

- Adverse event / Serious adverse event
- Protocol deviation
- Intolerability of injections
- Participant lost to follow-up
- Participant or Investigator non-compliance;
- Termination of the study by the Sponsor
- At the request of the participant, Investigator, GSK or ViiV Healthcare;

- The participant requires concurrent prohibited medications during the course of the study. The participant may remain in the study if in the opinion of the Investigator and the medical monitor; such medication will not interfere with the conduct or interpretation of the study or compromise the safety of the participant.

Participants must be discontinued from study treatment for any of the following reasons:

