- Participants who are not eligible to continue into the Maintenance Phase.
- Participants who are not eligible, or do not wish to continue on to the Extension Phase.
- Virologic withdrawal criteria as specified in Section 5.5.4 are met;
- Participant requires substitution of ART;
- Participant requires substitution or dose reduction of CAB LA or RPV LA (oral bridging supply and potential for a second loading dose may be permissible following discussion with the Medical Monitor).
- Liver toxicity where stopping criteria are met and no compelling alternate cause is identified (see Section 5.5.1);
- Renal toxicity are met and no compelling alternate cause is identified;
- QT interval (QTc) interval >550 msec from three or more tracings separated by at least 5 minutes and considered causally related to IP.
- Grade 4 clinical AE considered causally related to study drug;
- Participant has a Grade 3 or higher rash or Grade 2 rash with evidence of systemic involvement and no compelling alternative cause is identified
- Pregnancy (intrauterine), regardless of termination status of pregnancy.
- Participant withdrew consent

Efficacy data for participants withdrawing from the study will be considered evaluable up to the point at which they are withdrawn using the same criteria for evaluability as for participants who complete the study.

Safety data for all participants who receive any amount of study drug, including participants who withdraw from the study, will be included in evaluations of safety.

All data from the Withdrawal visit will be recorded, as they comprise an essential evaluation that should be done prior to discharging any participant from the study.

The following actions must be taken in relation to a participant who fails to attend the clinic for a required study visit:

- a. The site must attempt to contact the participant and re-schedule the missed visit as soon as possible.

- b. The site must counsel the participant on the importance of maintaining the assigned visit schedule and ascertain whether or not the participant wishes to and/or should continue in the study.

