5.5.2. QTc Stopping Criteria

A participant who has a QTc interval >550 msec considered causally related to IP will be withdrawn from the study. The QTc should be based on averaged QTc values of triplicate electrocardiograms obtained over a brief (e.g., 5 to 10 minute) recording period.

If an alternative cause of the QT prolongation is determined (e.g., participant receiving drug known to cause prolonged QT or TdP), the IP may be restarted (or continued) after

consultation and agreement with the Medical Monitor. RPV and RPV LA should not be administered to patients who are receiving a drug known to be associated with TdP.

When performing ECGs, the *same* QT correction formula *must* be used for *each individual participant* to determine eligibility for, and discontinuation from, the study. This formula may not be changed or substituted once the participant has been enrolled.

For example, if a participant is eligible for the protocol based on QTcB, then QTcB must be used for discontinuation of this individual participant as well.

Once the QT correction formula has been chosen for a participant's eligibility, the *same formula* must continue to be used for that participant *for all QTc data being collected for data analysis*. Safety ECGs and other non-protocol specified ECGs are an exception.

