7.4.5.9. QTc Prolongation

Participants with an average QTc interval >550 msec from three or more tracings separated by at least 5 minutes should have IP discontinued. These criteria are based on an average QTc value of triplicate ECGs. If an ECG demonstrates a prolonged QT interval, obtain 2 more ECGs over a brief period (~5-10 minutes) and use the averaged QTc values of the 3 ECGs to determine whether the participant should be discontinued from the study. If an alternative cause of the QT prolongation is determined (e.g., participant receiving drug known to cause prolonged QT or TdP), then IP may be restarted after consultation with, and agreement by, the Medical Monitor.

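### Section 5.5.2 bars rilpivirine for anyone taking a torsade-associated drug, yet Section 6.13.1 permits those drugs with caution and Section 6.13.2 never names them

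*Protocol*

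**What the plan says.** Five places in the protocol bear on a participant who takes a TdP-associated drug.

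- Section 5.2, exclusion criterion 38, makes this exclusionary at entry: "Use of medications which are associated with Torsade de Pointes". It refers to the Study Procedures Manual (SPM) for the list of drugs.
- Section 5.5.2, on QTc stopping, deals with a QTc above 550 msec that has another explanation. Its example is a "participant receiving drug known to cause prolonged QT or TdP), the IP may be restarted (or continued"), subject to agreement with the Medical Monitor. The next sentence reads: "RPV and RPV LA should not be administered to patients who are receiving a drug known to be associated with TdP".
- Section 6.13 allows concomitant drugs at the investigator's "discretion (except for prohibited medications described in Section 6.13.2) and should be administered only as medically necessary during the study".
- Section 6.13.1, on permitted drugs, says: "Drugs with a known risk of Torsade des Pointes (TdP) should be used with caution when on rilpivirine". It again points to the SPM for the list.
- Section 7.4.5.9 repeats the QTc rule with the same example and ends: "then IP may be restarted after consultation with, and agreement by, the Medical Monitor". It does not carry the bar on rilpivirine.

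Sections 6.13.2, 6.13.2.1 and 6.13.2.2 name no TdP or QT-prolonging drugs.

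**The concern.** The decision to prescribe a concomitant drug is made from Section 6.13. The bar on giving rilpivirine sits elsewhere, in a section on QTc stopping. A site that looks up a new drug in the medication chapter finds it allowed with caution, and Section 6.13.1 attaches no action to that caution: no ECG, no contact with the Medical Monitor, no preferred alternative. The site can then give the next injection in good faith and contravene Section 5.5.2.

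An error here is hard to undo. Section 6.9.1 notes that both long-acting drugs may be measurable for more than a year after injection, so holding a dose does not end co-exposure. The rule has to be clear before the second drug is started.

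**Working it through.** There is no figure to reproduce; the check is a comparison of texts.

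**Case 1: a TdP-associated drug is prescribed on study, QTc is normal, and an injection is due.**

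1. Section 6.13: is the drug prohibited under Section 6.13.2? It is not named, so it falls to the investigator's discretion.
2. Section 6.13.1: the drug may be used, with caution.
3. Section 5.5.2: rilpivirine should not be given to a person receiving it.

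Steps 2 and 3 give different answers about the same dose. Both use *should*, so neither outranks the other by strength of wording.

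**Does anything else in the protocol settle Case 1?**

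- Criterion 38 applies at entry only. It agrees with Section 5.5.2, which makes the Section 6.13.1 sentence the odd one out.
- Section 6.13.2 has a clause on drugs with potential for adverse interactions, but it sits in the bullet on hepatitis C therapy and mentions neither TdP nor QT. Stretching it to these drugs would make Section 6.13.2 prohibit what Section 6.13.1 permits.
- Section 6.13.2.1 has a rilpivirine-specific list, limited to proton pump inhibitors and repeated systemic dexamethasone. Section 6.13.2.2 adds anticoagulants.
- Where TdP drugs are mentioned, the protocol cites the SPM for a list. It does not say that the SPM decides which sentence governs.
- Section 6.13 says to contact the Medical Monitor with questions. A site that has read Section 6.13.1 has an answer and no evident question.

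Nothing shown resolves it.

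**Case 2: QTc exceeds 550 msec and a TdP-associated drug is the explanation.**

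1. Section 5.5.2 allows study drug to be restarted or continued with the Medical Monitor's agreement, then states the bar.
2. These can be read together. Injections are 4 or 8 weeks apart, so if the TdP drug is stopped before the next one, treatment continues and the bar is respected. The example also covers drugs that prolong QT without being associated with TdP, and the bar does not reach those.
3. The text does not say that the TdP drug must be stopped first, and Section 7.4.5.9 omits the bar.

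Case 2 is a gap in wording. Case 1 is the contradiction.

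**The case against.** The best defence is context. The bar in Section 5.5.2 follows directly on the restart rule for a QTc above 550 msec. It may be meant only for that situation, with Section 6.13.1 as the general rule. This is a possible reading, and the documents do not show which was intended. But the sentence speaks of patients receiving a TdP-associated drug, without reference to QTc. The narrow reading also leaves a drug that disqualifies a person at entry permitted once that person is enrolled.

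A second defence is that guidance may lie outside the protocol. The SPM is not shown, and Section 6.13.1 also sends sites to local rilpivirine prescribing information for drugs that are prohibited or need caution. That stands as a limit on this review. It does not reconcile two protocol sentences.

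Three stronger readings are tempting, and the documents do not support them.

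- A reader might infer that the words *or continued* in Section 5.5.2 flatly contradict the bar. Case 2 shows that they need not.
- A reader might infer that Section 7.4.5.9 contradicts Section 5.5.2. It only leaves the bar out, and Section 7.4.10 refers to Section 5.5.2 for the QTc withdrawal criteria.
- A reader might infer a conflict over who decides: the investigator under Section 6.13, or the investigator and Medical Monitor together under the Section 5.5 item "The participant requires concurrent prohibited medications during the course of the study". That item concerns prohibited drugs. TdP drugs are not on the prohibited list, so it does not reach them.

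**Conclusion.** Wrong as written: an internal contradiction in a safety rule, which should be corrected. Sections 5.5.2 and 6.13.1 give opposite instructions on dosing rilpivirine when a TdP-associated drug is started on study, and nothing else in the protocol decides between them. The finding rests on reading the Section 5.5.2 sentence as generally as it is worded.

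The people concerned are those newly prescribed such a drug during treatment of at least 100 weeks; users at entry are excluded. How many that would be cannot be derived from the protocol. Both arms receive rilpivirine. A reader might infer from the Snapshot rules that the present wording threatens the primary analysis, but nothing in the documents shows this.

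**What to change.** Adopt one rule, in line with Section 5.5.2 and criterion 38.

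1. **Section 6.13.1:** replace the sentence on caution. TdP-associated drugs (SPM list) should not be started while oral or long-acting rilpivirine is being dosed; an alternative should be used; the Medical Monitor must be contacted before an unavoidable one is started. Note that long-acting rilpivirine exposure persists after dosing is held.
2. **Section 5.5.2:** add the same Medical Monitor exception to the bar. Otherwise an unconditional bar would still conflict with the new Section 6.13.1.
3. **Section 6.13.2:** cross-refer to this rule. Do not add the drugs to the list itself, because that list is headed as never permitted during the study and the rule allows an exception.
4. **Sections 5.5.2 and 7.4.5.9:** state that, where a TdP drug explains the QT prolongation, rilpivirine is next dosed only after that drug is stopped and the Medical Monitor agrees. The words *or continued* may stay for other causes.

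Criterion 38 needs no change. Limiting the Section 5.5.2 bar to QTc events would take fewer edits, but it would keep the mismatch with criterion 38.

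The cost is wording in four sections of one amendment. A few participants may need a different drug or a dosing interruption. Unavoidable cases should be handled individually and not by automatic change of antiretroviral therapy, because Section 5.5 lists "Participant requires substitution of ART" among the reasons for mandatory discontinuation of study treatment.
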